11.2. Reporting of Adverse Events

Assessment of the occurrence of an AE will be based on changes in the subject’s physical examination, laboratory results and/or signs and symptoms. Adverse events will be monitored until a subject completes the study. Medical care will be provided, as defined in the informed consent, for any AE related to study participation. Adverse events will be collected on an AE CRF and applicable source documentation. To the extent possible, the event to be recorded and reported is the event diagnosis as opposed to event symptoms (e.g., fever, chills, nausea and vomiting in the presence of a clinically diagnosed infection is to be reported as infection only). For the purposes of this protocol, only those AEs occurring after enrollment will be recorded.

The following should not be considered an AE:

- A condition requiring a preplanned procedure unless the condition worsened since enrolment
- A preexisting condition found as a result of screening, unless the condition has worsened since enrollment.

All responses to the above events that require treatment beyond the institution's standard procedures will be reported as AEs.

All AEs observed during the course of this study, regardless of severity or relationship to the device will be recorded on the appropriate CRF.

Notification to Authorities

The following events are generally considered reportable during the course of this study and should be reported to the sponsor:

- any AE, ADE, SADE, USADE, or SAE
- any Device Deficiency
- new findings/updates in relation to already reported events.

Type	Report to	Reporting Timeframe (from time of learning of event)
Device Deficiency	Sponsor	Within 48 hours
AE/ ADE	Sponsor	Recommended within 10 working days
	IRB/EC	Per IRB/EC reporting requirements
SAE/ SADE/USADE	Sponsor	Within 24 hours
	IRB/EC	Within 10 working days, unless stricter reporting is required by local regulations or IRB/EC
DD with SADE potential	Sponsor	Within 24 hours
	IRB/EC	Within 10 working days, unless stricter reporting is required by local regulations or IRB/EC
Death	Sponsor	Within 24 hours
	IRB/EC	Required within 10 working days, unless stricter reporting is required by local regulations or IRB/EC

Medtronic Confidential

- Events will be reviewed by sponsor or designee to determine any reporting obligations to National Competent Authorities and IRB/EC.
- According to the CFDA Notice No. 766-2008, Provisions of Adverse Events Surveillance and Reevaluation of Medical Device (Trial),
 - 1) Death events should be reported to the local provincial technical institution of medical device adverse events surveillance within 5 working days;
 - 2) Events led to serious injury or potentially led to serious injury or death, should be reported to the local provincial technical institution of medical device adverse events surveillance within 15 working days.

Any Adverse Event will be recorded on the **Adverse Event CRF**.

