7.2. The Barrx™ Circumferential Radiofrequency Ablation System

The Barrx™ Circumferential Radiofrequency Ablation System includes an energy generator (Model 1190A-115A), ablation catheters (Model 32041-18, 32041-22, 32041-25, 32041-28, 32041-31), and sizing balloons (Model 3441C). The circumferential ablation catheters will be used for independent treatment or main treatment. The energy generator is used to inflate a sizing balloon positioned within the esophageal body, in order to measure the inner diameter of the targeted portion of the esophagus. Upon determination of the inner diameter size (mm), an appropriately sized ablation catheter is selected for ablation. The ablation catheter has a balloon at its distal end, wrapped with an electrode having tightly spaced bipolar electrode bands. The generator inflates this ablation catheter within the esophagus and delivers the controlled amount of RF energy to achieve the desired ablation effect. At

the recommended energy density and number of applications, the maximum depth of ablation in previous studies is the muscularis mucosae.

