8.2. Subject Enrollment

Up to 100 subjects are planned for enrollment in the primary analysis cohort. With up to 10 sites and 1-2 endoscopists at each site, up to 50 'run-in' patients will be included in this study. Run-in patients are defined as up to 5 patients for each endoscopist that is inexperienced with RFA or has had no RFA onsite training from CICAMS. Data from the run-in patients will be analyzed separately from the cohort.

Patients shall be reviewed according to the following inclusion and exclusion criteria. An answer of "no" to any inclusion criterion or an answer of "yes" to any exclusion criterion disqualifies a subject from participating in this study. Complete the **Eligibility CRF**.

Definitive eligibility can only be assured during the primary RFA endoscopy, e.g. if a severe stricture or a non-flat abnormality is present, patient is not eligible. Therefore, the subject is considered as enrolled after insertion of the RFA catheter.

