9.1. Schedule of Events

For patients who meet all of the inclusion criteria and none of the exclusion criteria, step-wise endoscopic RFA will be performed in 3month intervals \pm 4 weeks from the first RFA per the Patient Flow Diagram (Figure 1). Each decision point in the flow diagram regarding endoscopy, staining, RFA, biopsy, and patient advancement to subsequent study visits is fully delineated in the diagram. The study primary endpoint biopsies are obtained at 12 months from the initial treatment.

Study procedures are summarized in Table 2 and described in detail below.

Table 2. Study Schedule and Assignments

	BQE (1 week to 3 months before first RFA)	Baseline assessmen ts	Primary RFA	3-Month Follow-Up visit (from primary RFA, \pm 4 weeks)	6-Month Follow-Up Visit (from primary RFA, \pm 4 weeks)	9-Month Follow-Up Visit (from primary RFA, \pm 4 weeks)	12-Month- Primary Endpoint (from primary RFA, \pm 4 weeks)	2-3-4-5 Year Follow-up (from primary RFA, \pm 4 weeks)
	BQE is part of regular care		After insertion of RFA catheter, patient is considered enrolled in the study: treatment phase					Follow-up phase
Informed Consent		X						
Patient History CRF		X						
Baseline Qualifying CRF		X						
Confirmation of Study Eligibility CRF		X						
Upper Endoscopy using Lugol's Solution	X			X	X	X	X	X
Circumferential RFA at 12 J/cm ²			X					
Endoscopy CRF			X	X	X	X	X	X
Table of findings CRF			X	X	X	X	X	X

Medtronic Confidential

COVB3050540 (REACH) Clinical Investigation Plan

Version 7.0

15-Mar-2018

Page 26 of 62

	BQE (1 week to 3 months before first RFA)	Baseline assessmen ts	Primary RFA	3-Month Follow-Up visit (from primary RFA, +/- 4 weeks)	6-Month Follow-Up Visit (from primary RFA, +/- 4 weeks)	9-Month Follow-Up Visit (from primary RFA, +/- 4 weeks)	12-Month- Primary Endpoint (from primary RFA, +/- 4 weeks)	2-3-4-5 Year Follow-up (from primary RFA, +/- 4 weeks)
Circumferential or focal RFA at 12 J/cm ²				X	X	X		X
Biopsy	X			X	X ¹	X ¹	X	X
Central pathology review (BQE biopsy)		X						
Central pathology review				X	X	X	X	X
2 nd pathologist assessment		X					X	X ²
Pathology CRF		X		X	X	X	X	X
Study Exit CRF								X ⁴
Safety Assessment			X	X	X	X	X	X
Observation of endoscopy by CICAMS expert			X	X	X	X	X	X
Keyhole biopsy if diagnosis of suspicious/visible lesion needed before escape treatment				X	X	X	X	X
Escape treatment (see section 9.4.3) for ESCC/ disease suspicious for ESCC				X	X	X		X

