9.3. Subject Consent

If the subject is deemed eligible after BQE and medical record reviewing, the research team member may then approach the potential subject to discuss participation in the study, including background of the proposed study, inclusion and exclusion criteria, the benefits and risks of the procedures and the follow-up requirements. If the study is of interest to the subject, the informed consent form (ICF) will be discussed and presented. The subject must sign the ICF prior to enrollment. This form must have prior approval of institutional review board (IRB)/ ethics committee (EC) for all participating sites. Failure to obtain informed consent will render the subject ineligible for the study.

Patients will be approached to obtain written informed consent prior to any study specific procedures being performed. The purpose of the study and the benefits and risks of the procedures will be explained to the subject in their local language. The consent process must be documented accordingly in the medical record. Patients who agree to study participation must sign an IRB/EC-approved ICF. Subjects will be informed that their participation in this study is voluntary and they may refuse to participate or discontinue from the study at any time. Subjects will be given the opportunity to ask the investigator questions so that they are adequately informed about the research. A copy of the signed informed consent must be provided to the subject and the informed consent process will be documented in source documents.

If new information becomes available that may affect a subject's decision to continue to take part in the study, this information will be discussed with the subject by the investigator.

Subjects will be assured that they may withdraw from the study at any time for any reason.

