11.1. Definitions/Classifications

Adverse Events

Adverse event (AE) definitions used in this study are based on ISO 14155:2011 (Clinical Investigation of Medical Devices for Human Subjects -- Good Clinical Practice). Adverse events will be collected starting from enrollment into the study.

Adverse Event (AE)

An Adverse Event is any untoward medical occurrence, unintended disease or injury, or untoward clinical signs (including abnormal laboratory findings) in subjects, users or other persons, whether or not related to the investigational medical device.

NOTE 1 This definition includes events related to the investigational medical device or the comparator.

NOTE 2 This definition includes events related to the procedures involved.

NOTE 3 For users or other persons, this definition is restricted to events related to investigational medical devices.

Serious Adverse Event (SAE)

A Serious Adverse Event is an adverse event that has

a) Led to death,

b) Led to serious deterioration in the health of the subject, that either resulted in

1) A life-threatening illness or injury, or

Medtronic Confidential

- 2) A permanent impairment of a body structure or a body function, or
- 3) In-patient or prolonged hospitalization, or
- 4) Medical or surgical intervention to prevent life-threatening illness or injury or permanent impairment to a body structure or a body function,

c) Led to fetal distress, fetal death or a congenital abnormality or birth defect

NOTE: Planned hospitalization for a pre-existing condition, or a procedure required by the clinical investigational plan, without serious deterioration in health, is not considered a serious adverse event.

Adverse Device Effect (ADE)

An Adverse Device Effect is an adverse event related to the use of an investigational medical device.

NOTE 1 This definition includes adverse events resulting from insufficient or inadequate instructions for use, deployment, implantation, installation, or operation, or any malfunction of the investigational medical device.

NOTE 2 This definition includes any event resulting from use error or from intentional misuse of the investigational medical device.

Serious Adverse Device Effect (SADE)

A Serious Adverse Device Effect is an adverse device effect that has resulted in any of the consequences characteristic of a serious adverse event.

Unanticipated Serious Adverse Device Effect (USADE)

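### Adverse-event recording and the safety set both start at RFA-catheter insertion, after the consented patient has been marked and balloon-sized, so a patient stopped before insertion is outside the safety analysis

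*Protocol*

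**What the plan says.** Protocol section 11.1 sets the start of collection: "Adverse events will be collected starting from enrollment into the study". Section 11.2 makes this exclusive: "only those AEs occurring after enrollment will be recorded". Section 8.2 defines the event that starts the clock: "the subject is considered as enrolled after insertion of the RFA catheter". The note in Table 2 (section 9.1) repeats it: "After insertion of RFA catheter, patient is considered enrolled in the study". Protocol section 13.3 and SAP section 7.1.3 use the same definition, and both limit the safety analysis to enrolled subjects.

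Consent comes earlier. Section 9.3 states: "Patients will be approached to obtain written informed consent prior to any study specific procedures being performed". The numbered steps of the primary session are in section 9.4.1. Section 7.2 explains what measuring involves: "The energy generator is used to inflate a sizing balloon positioned within the esophageal body". It lists the sizing balloon as a component of the circumferential system, separate from the ablation catheters, and has the catheter chosen only once the diameter is known.

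The adverse-event definition in section 11.1 is not confined to ablation. Its Note 2 reads: "This definition includes events related to the procedures involved".

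**The concern.** The recording window and the safety set open partway through an invasive session. An injury from marking or balloon sizing is an adverse event under the protocol's own definition, and a sizing-balloon injury can also be an adverse device effect, yet it falls before the window.

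The protocol expects some patients to stop at this point. Section 8.2 says that eligibility can be settled only during the primary RFA endoscopy, and section 9.4.1 excludes a patient at step 5 if the measured diameter is below 18 mm, after both marking and sizing.

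The possible loss runs one way: such events can be missed but not over-counted. Safety is a stated secondary objective. Under protocol section 13.5 and SAP section 7.10, a single perforation, or a single mucosal laceration that needs intervention, is enough to prompt a review by the medical advisors. The secondary endpoint on serious adverse device effects (protocol 5.2.2, SAP 7.9.2) counts events following RFA treatment without saying when that period begins, so it does not settle whether a sizing-balloon injury counts.

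**Working it through.** **1. Order of the primary session (protocol 9.4.1) against the enrolment definition (8.2)**

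| Step | Action | Enrolled yet? | Can participation end here? |
|---|---|---|---|
| 1 | White-light endoscopy | No | Findings feed step 3 |
| 2 | Lugol's staining | No | Findings feed step 3 |
| 3 | Definitive eligibility check | No | Yes |
| 4 | Electrocoagulation marking | No | Not stated |
| 5 | Measuring with the sizing balloon (7.2) | No | Yes, diameter below 18 mm |
| 6 | Circumferential RFA | Yes, once the catheter is in | – |

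Consent precedes step 1. A patient stopped at step 3 or step 5 has consented and had study procedures, but is never enrolled.

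**2. What each provision does for an injury at steps 1 to 5**

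| Provision | Gets the injury recorded? | Puts a stopped patient in the safety set? |
|---|---|---|
| 11.1 and the exclusive sentence in 11.2 | No, read literally | No |
| Two broader sentences in 11.2 (all adverse events observed during the study; any adverse event goes on the form) | Yes, unless limited by the exclusive sentence | No |
| Sponsor-notification list in 11.2 | Reaches the sponsor; no enrolment condition stated | No |
| Safety Assessment row, Table 2, primary RFA column | Possibly; no start point given | No |
| Endoscopy form, end of the primary RFA steps in 9.4.1 | As procedure data | No |
| Device deficiencies, 11.3 | Only if a deficiency, such as malfunction or use error, led to the event | No |
| 13.3 and SAP 7.1.3 | – | No, enrolled subjects only |

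The middle column is mixed. The right-hand column is not.

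**3. The plan's own safety figures**

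Protocol 13.2 and SAP 6 give the chance of seeing at least one event in 100 subjects. The formula is 1 − (1 − p)^100.

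- p = 0.05: 1 − 0.95^100 = 0.9941 (stated: above 99%).
- p = 0.02: 1 − 0.98^100 = 0.8674 (stated: 85%).

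Both reproduce, the second to within two percentage points. They describe events that are recorded in enrolled subjects and are not in dispute.

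**4. Illustration: one perforation at sizing that ends the session**

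The inputs are up to 100 cohort subjects and up to 50 run-in subjects (8.2). The one event is assumed. Exact (Clopper-Pearson) 95% limits:

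- For 0/n, the upper limit is 1 − 0.025^(1/n).
- For 1/n, the lower limit is 1 − 0.975^(1/n), and the upper limit solves (1 − p)^n + np(1 − p)^(n−1) = 0.025.

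| Population | Enrolled-only set | Set that includes the stopped patient |
|---|---|---|
| Cohort | 0/100: 0% (0 to 3.62%) | 1/101: 0.99% (0.025 to 5.39%) |
| Cohort plus run-in | 0/150: 0% (0 to 2.43%) | 1/151: 0.66% (0.017 to 3.63%) |

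**5. Range under assumed incidences**

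The documents give neither a rate of injury before insertion nor a number of patients stopped. Suppose 100 cohort subjects reach insertion, 0 to 10 more are stopped, and the injury rate at marking or sizing is 1%, 2% or 5%. The expected number of injuries before the window is rate × (100 to 110): 1.0 to 1.1, 2.0 to 2.2, or 5.0 to 5.5. These are all such injuries on the literal reading, before any of the partial routes in item 2 is allowed for.

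**The case against.** A reader might go further and infer that injuries at marking or sizing cannot be recorded at all, or that a perforation at sizing could not prompt the safety review. The documents do not support that.

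- Section 11.2 also says, in two places, that adverse events are to be recorded without an enrolment condition. A sizing injury fits neither of the categories which that section says are not adverse events.
- The sponsor-notification list in 11.2 has no enrolment condition, and serious events go to the sponsor within 24 hours. Serious injuries also have a provincial reporting route.
- The endoscopy form takes all data from the procedure, and SAP 7.7 summarises procedure and endoscopy data.
- Section 9.9 lets the endoscopist withdraw a subject and record the reason and any relation to the device. Whether this reaches a consented patient who is not yet enrolled is arguable.
- The review in 13.5 and SAP 7.10 is not tied to the safety set, and the advisors look at all available data. An event known to the sponsor could be raised under the present wording.
- A patient who goes on to insertion is enrolled, and later worsening can then be recorded.

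All of this stands, and it reduces the recording problem to a conflict within section 11.2 with partial capture around it. It does not reach the analysis set: none of these provisions makes a patient stopped before insertion an enrolled subject.

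The term RFA catheter might also be stretched to include the sizing balloon. Section 7.2 lists the two separately and selects the catheter after sizing, and marking would come before either.

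Finally, the illustrated intervals overlap heavily, and the affected group may be very small. That limits the size of the problem but does not remove the gap.

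**Conclusion.** The point holds in a limited form. Taken literally, the exclusive sentence in 11.2 leaves out injuries at steps 1 to 5 of the primary session. It conflicts with broader sentences in the same section, so sites could reasonably act differently. Separately, and without ambiguity, a consented patient stopped before catheter insertion is outside the safety set in both documents. An injury in that patient would be missing from the safety tables and rates, and it might not be raised for review.

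The size is unknown. The 0/100 against 1/101 comparison shows what a single event would do; it is not an estimate. The gap is confined to the primary session. The primary effectiveness endpoint, the stated precision and the stated detection probabilities are unaffected. The conclusion rests on reading RFA catheter as the ablation catheter, as section 7.2 does. It should be fixed because a single event can matter under the review rule and the repair is only wording.

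**What to change.** Use one start point throughout: the start of the primary RFA endoscopy in a consented subject.

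- **Protocol 11.1 and 11.2:** record adverse events from that point, and align the exclusive sentence and the two broader sentences with it.
- **Protocol 13.3 and SAP 7.1.3:** define the safety set as all consented subjects, cohort and run-in, in whom the primary RFA endoscopy was begun. Report the number stopped before catheter insertion, with reasons.
- **Protocol 5.2.2 and SAP 7.9.2:** state that the endpoint on serious adverse device effects includes sizing-balloon events in that session.
- **Effectiveness:** keep catheter insertion as the enrolment point for the cohort.

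The safety set should not start later than recording, for example at marking. A patient injured during white-light endoscopy or staining and stopped at step 3 would then have a recorded event but no place in the analysis.

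The cost is protocol and SAP wording, a few extra adverse-event forms, and possibly slightly higher event counts. The safety denominator also becomes slightly larger and includes some patients who were never ablated, which dilutes rates of ablation-related events. Showing those patients separately as well deals with this.

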11.3. Device Deficiencies

A device deficiency is an inadequacy of a medical device related to its identity, quality, durability, reliability, safety, or performance, such as malfunction, misuse or use error and inadequate labeling.

All device deficiencies will be documented on the Device Complaint CRF (1 for each Device Deficiency), and the device should be returned to the Sponsor for analysis, if possible. Instructions for returning the device will be provided. Device deficiencies should also be documented in the subject's medical record.

Device Deficiencies that led to an AE are reported on the AE CRF and the Device Complaint CRF.

12. Data Review Committees

Independent Medical Advisors

The Sponsor will utilize Independent Medical Advisor(s) to provide an independent medical review and adjudication of pre-specified adverse events in support of protocol defined endpoint data. The Independent Medical Advisor(s) will be qualified, board-certified physicians.

During the review of adverse events or overall study utility, efficacy, and safety data, the Independent Medical Advisor(s) will be blinded to the investigational site.

13. Statistical Design and Methods

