Sample Size	Up to 100 subjects will be included in the cohort, in up to 10 clinical sites. This is excluding up to 50 “run-in” subjects, defined as up to 5 patients for each endoscopist that is inexperienced with RFA or has had no onsite RFA training from CICAMS. Data from the run-in patients will be analyzed separately from the cohort.
Inclusion/Exclusion Criteria	Inclusion Criteria

Medtronic Confidential

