13.3. Analysis Populations

The primary analysis will be based on a per-protocol basis. Subjects who enrolled into the study (a patient is defined as enrolled after introduction of RFA catheter at primary RFA), and had valid study outcomes with no major protocol violations will be included in the analysis. Only the 100 cohort patients will be included for primary analysis.

Additional analyses based on subsets of the study subjects or combining run-in subjects may be performed to provide further support to the study results.

All enrolled study subjects will be included in the safety analysis.

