13.5. Safety Analysis

For safety analyses, adverse events will be summarized using frequency counts and percentages. Descriptive statistics will be provided by event type, severity and relationship to study procedures and devices. Event rates along with 95% confidence intervals will be provided based on subject or event. Individual listings of adverse events, including event type, start date, duration, severity, and device-relatedness will be provided as appropriate.

Safety will be closely monitored during the course of the study. If the incidence of severe or serious adverse events is higher than expected (stricture/stenosis requiring dilation >10%, any mucosal laceration requiring intervention, any perforation, any bleed or infection requiring intervention, or any other severe or serious unexpected adverse event), or a statistically significant trend is observed, the medical advisors will notify the sponsor, review all available data, and make a recommendation regarding continuation of the study.

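### The advisors who recommend on continuation are blinded to site, so they cannot see whether complications cluster in one site or operator

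*Protocol*

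**What the plan says.** Protocol Section 12 (Independent Medical Advisors) gives the advisors the adjudication of pre-specified adverse events. It then sets the blinding, whose scope is wider than adjudication: "During the review of adverse events or overall study utility, efficacy, and safety data", "the Independent Medical Advisor(s) will be blinded to the investigational site".

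Protocol 13.5, repeated in SAP 7.10, lists what counts as a higher incidence than expected. One item is a rate: "stricture/stenosis requiring dilation >10" per cent. Others need one case, among them "any perforation, any bleed or infection requiring intervention", a laceration that needs intervention, and any other unexpected severe or serious event. An undefined statistically significant trend is also listed. If any of these is met, "the medical advisors will notify the sponsor, review all available data, and make a recommendation regarding continuation of the study". Neither section says whether site is unmasked at that point.

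The plan treats results as dependent on the operator. It sets aside run-in subjects, "up to 5 patients for each endoscopist that is inexperienced with RFA" or lacking onsite CICAMS training. It has a CICAMS expert observe endoscopies (Protocol 7.5) and plans learning-curve summaries by site (Protocol 13.6, SAP 7.11). Protocol 6.2 reports that the authors of the first cited study thought technique and dose may contribute to strictures.

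**The concern.** The trial has one arm and is open, so blinding to site protects no treatment comparison. It does protect the adjudication of a single event from what the adjudicator thinks of a hospital. For a judgement about the whole study it has a cost: a run of complications from one endoscopist looks the same as the same number scattered over ten sites. Those two patterns call for different recommendations, and the people asked to recommend lack the variable that separates them.

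For strictures there is a second effect. The trigger is one percentage with no site-level version, so a high rate at a small site is averaged with the rest.

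**Working it through.** **Setting the sections side by side.** Section 12 withholds site from the review of overall safety data. Section 13.5 has the medical advisors (read here as the same people) review all data and recommend. Both cannot be followed literally.

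**The plan's own safety figure.** Protocol 13.2 and SAP 6 give the chance that 100 subjects show at least one event: above 99% at 5% incidence and 85% at 2%. Recomputed: 1 − 0.95^100 = 99.4% and 1 − 0.98^100 = 86.7%. The figures reproduce to within 2 points. They concern an event occurring somewhere, not where it occurs.

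**Inputs for the stricture trigger.**
- Size: "Up to 100 subjects will be included in the cohort, in up to 10 clinical sites", so 10 per site on average if all are used.
- Rate elsewhere: 6%, reported in Protocol 6.2 for this regimen on 17 patients (1/17 = 5.9%). An alternative of 3% is an assumption.
- Rate at the one outlying site: 30%, 40% or 50% (assumptions).
- Trigger: pooled over subjects, strictly above 10%, so at least 11 of 100 or 16 of 150.

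**Formula.** Total strictures = Binomial(90, 0.06) + Binomial(10, q), with P(total ≥ 11) by exact convolution. The expected pooled rate is (5.4 + 10q)/100.

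| Site rate q | Expected pooled rate (6% elsewhere) | P(trigger), 10 of 100, 6% elsewhere | P(trigger), 10 of 100, 3% elsewhere | P(trigger), 15 of 150, 6% elsewhere |
|---|---|---|---|---|
| 30% | 8.4% | 21% | 2% | 19% |
| 40% | 9.4% | 33% | 5% | 33% |
| 50% | 10.4% | 47% | 11% | 50% |

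The pooled expectation reaches 10% only at q = (10 − 5.4)/10 = 46%, or (10 − 2.7)/10 = 73% with 3% elsewhere.

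**Site size matters.** For a site of 20 among 100 at 40%, the expectation is (0.06×80 + 0.40×20)/100 = 12.8% and P(trigger) is 77%. For one operator's 5 run-in subjects at 40% among 150, P(trigger) is 6%, against 1.9% with no outlier.

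**One concrete table.** With 4/10 at one site and 6/90 elsewhere, the total is 10/100 = 10.0%, which is not above 10%. Fisher's exact test on that split gives p = 0.008. That p-value takes the site as given; a Bonferroni correction for choosing the worst of ten gives 10 × 0.008 = 0.08. Either way the pattern merits a look, and site-blinded advisors cannot see it.

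**Information in a by-site table.** As a measure only, not a proposed rule: the chance that a site of 10 shows three or more strictures is 62%, 83% and 95% at 30%, 40% and 50%. At 6% it is 1.9% per site, or 1 − (1 − 0.0188)^10 = 17% for at least one of ten sites.

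**Single-event triggers.** These cannot be diluted. If 20% of subjects at a site of 10 have such an event, review is prompted with probability 1 − 0.8^10 = 89%, whatever happens elsewhere.

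**The case against.** A reader might infer that a dangerous site can stay below the study-wide trigger for any complication. The trigger list does not support that: perforation, and laceration, bleeding or infection needing intervention, prompt review on one case. Only strictures requiring dilation can be averaged away.

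A reader might also infer that the study as a whole cannot see a bad site. It can. Serious events reach the sponsor within 24 hours (Protocol 11.2), a CICAMS expert observes endoscopies, and 13.6 plans by-site summaries that include serious adverse device effects. The sponsor, not the advisors, holds power over an investigator. This stands. What it leaves open is that no section sends the site-level data to the advisors or says who escalates a site-level rate.

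The dilution comes from pooling, not from blinding: unblinded advisors would face the same 10%. That is also right. The table above shows how often the rate trigger would not prompt a review. The blinding governs what the advisors can learn in any review they do hold, including the assessment after up to 50 patients and the summaries they may request under 13.6.

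The denominator of the 10% is unstated, and examples turn on it. With 15 subjects at 40% and 6% elsewhere, the expected rate is (6 + 8.1)/150 = 9.4% of all enrolled if every run-in place is filled, but (6 + 5.1)/100 = 11.1% of a 100-subject denominator. Protocol 13.3 says "All enrolled study subjects will be included in the safety analysis" but does not tie the trigger to that population.

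Finally, Section 12 masks site and is silent on endoscopist, run-in status and coded labels. Codes may be compatible with it, but nothing provides for them.

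**Conclusion.** The point holds in this form: the blinding reaches the safety and continuation review, conflicts with the instruction to review everything, and leaves the advisors unable to separate a device problem from an operator problem. For single-event triggers a review does start, but the advisors still could not tell that repeat cases share a site.

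For strictures, an average-sized site at 30% to 40% would more often than not leave the pooled figure at or below 10% (trigger probability 21% to 33%). That rests on ten equal sites, one outlier, a pooled trigger, assumed site rates and a 6% background from 17 patients. A large site is much less hidden. This is an inexpensive improvement to safety review and does not affect the primary estimate.

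**What to change.** 1. In Section 12, keep full site blinding for adjudication of individual events. For the overall safety and continuation review, state that the advisors receive events and denominators by coded site, coded endoscopist and run-in or cohort status, with names masked unless they ask.
2. Supply the by-site summaries of Protocol 13.6 to the advisors in that coded form.
3. Reconcile Protocol 12 with Protocol 13.5 and SAP 7.10, so that it is clear what the advisors see when they recommend.
4. State the denominator of the existing 10% figure.

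No new clinical threshold is proposed. The cost is a short amendment and tables from data already held. The small downside is that an advisor may guess a large site from its code.
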